6.3. Day 84±7 days

- (1) Conduct physical examination and record vital signs
- (2) Collect fasting blood sample for analysis of:
 - Hematology: CBC, including Hb, Hct, RBC count, WBC count, WBC differential and platelet count
 - Biochemistry: ALT, AST, ALP, total bilirubin, BUN, Serum Cr, electrolytes (K, Na, Mg, Ca and P), blood glucose, lipid profile (LDL, HDL, triglycerides)
 - PSA level
- (3) Collect urine sample for urinalysis test:
 - pH, specific gravity, leukocyte, erythrocyte, protein
- (4) Record concomitant medication(s)
- (5) Record AE(s)

6.4. Day 168±7 days

- (1) Conduct physical examination and record vital signs prior to dosing
- (2) Collect fasting blood sample prior to dosing for analysis of:
 - Hematology: CBC, including Hb, Hct, RBC count, WBC count, WBC differential and platelet count
 - Biochemistry: ALT, AST, ALP, total bilirubin, BUN, Serum Cr, electrolytes (K, Na, Mg, Ca and P), blood glucose, lipid profile (LDL, HDL, triglycerides)
 - PSA level
 - Testosterone Level (Optional item depending on investigators' judgment)
- (3) Collect urine sample prior to dosing for urinalysis test:
 - pH, specific gravity, leukocyte, erythrocyte, protein
- (4) Conduct 12-Lead ECG
- (5) Record concomitant medication(s) prior to dosing
- (6) Record AE(s) prior to dosing and post dosing
- (7) Administer LMIS 50 mg (second administration)

6.5. Day 252±7 days

- (1) Conducted physical examinations and record vital signs
- (2) Collect fasting blood sample for analysis of:
 - Hematology: CBC, including Hb, Hct, RBC count, WBC count, WBC differential and platelet count
 - Biochemistry: ALT, AST, ALP, total bilirubin, BUN, Serum Cr, electrolytes (K, Na, Mg, Ca and P), blood glucose, lipid profile (LDL, HDL, triglycerides)
 - PSA level
- (3) Collect urine sample for urinalysis test:
 - pH, specific gravity, leukocyte, erythrocyte, protein
- (4) Record concomitant medication(s)
- (5) Record AE(s)

6.6. Day 336±7 days (End of Study / Early Termination)

- (1) Conduct physical examination and record vital signs
- (2) Perform 12-lead ECG (5 minute supine)
- (3) Collect fasting blood sample for analysis of:
 - Hematology: CBC, such as Hb, Hct, RBC count, WBC count, WBC differential

and platelet count

- Biochemistry: ALT, AST, ALP, total bilirubin, BUN, Serum Cr, electrolytes (K, Na, Mg, Ca and P), blood glucose, lipid profile (LDL, HDL, triglycerides)
- HgbA1c
- PSA level

(4) Collect urine sample for urinalysis:

- pH, specific gravity, leukocyte, erythrocyte, protein

(5) Record concomitant medication(s)

(6) Record AE(s)

(7) Exit off the study

(8) For early termination subjects, phone contacts should be performed at 3 and 6 months after the last injection of study drug to collect drug-related AE, concomitant medication or non-drug therapy received for AE treatment, disease progression status, and subject survival status

7. Study Assessments

7.1. Screening assessment

7.1.1. Informed Consent form

The investigator or designee must explain to each subject the nature of the study, its purpose, the procedures involved, the expected duration, the potential risks and benefits involved and any potential adverse events. Each subject will be informed that participation in the study is voluntary and that he can withdraw from participation at any time.

All subjects must provide a signed and dated informed consent at the Screening Visit. An informed consent form approved by the Institutional Review Board (IRB), Ethics Committee (EC), and/or the applicable health authorities must be used.

7.1.2. Demographics / History

The demographic and baseline characteristics data for subjects collected under Protocol FP01C-13-001 will be updated at the Screening Visit and used as the data for this study. The demographics will include date of birth, age, gender and ethnicity.

The general medical history and tumor history collected for participation in Protocol FP01C-13-001 will be used for this study.

7.1.3. Eligibility

Eligibility should be thoroughly checked by the investigator at the Screening Visit. See Section 4.1 and 4.2, Inclusion and exclusion Criteria for details.

7.2. Safety Assessment

7.2.1. Physical Examinations and Vital signs

Subjects will be examined at the Screening Visit, Day 84 ± 7 days, Day 168 ± 7 days, Day 252 ± 7 days and Day 336 ± 7 days by standard physical examination including general appearance, skin, eyes, ear/nose/throat (ENT), head and neck, heart, chest and lungs, abdomen, extremities, lymph nodes, musculoskeletal, neurological, and other body systems if applicable for describing the status of the subject's health (Parts I and II).

Body weight will be measured. Body height in centimeters (cm) measured under Protocol FP01C-13-001 will be used for this study. Body weight will be measured at the Screening Visit and Day 336 ± 7 days to the nearest 0.1 kilogram (kg) or pound (lb.) in indoor clothing without shoes.

Vital signs will be measured at each visit, including resting (seated 3 minutes) blood pressures, heart rate, respiratory rate and body temperature.

*If the patient completed 12 months of treatment with LMIS 50 mg more than 28 days prior to entering the Extension study, the testosterone level should be repeated and the repeat test should indicate that the patient maintains a castrate-level of testosterone. In addition, the ECOG, PE, ECG, laboratory and PSA tests should be repeated.

If the patient has completed 12 months of treatment with LMIS 50 mg under Protocol FP01C-13-001 within the last 28 days, they will be allowed to enter the Extension study without repeating the testosterone measurements, ECG, PE, laboratory and the PSA tests.

7.2.2. Hematological / Biochemistry Examinations

Fasting blood samples will be collected for hematological, biochemistry and biological examinations.

Hematological tests will include complete blood count (CBC), including hemoglobin (Hb), hematocrit (Hct), red blood cells (RBC), white blood cells (WBC), WBC differential (neutrophils, eosinophils, basophils, lymphocytes and monocytes) platelet counts and HgbA1c. Biochemistry tests will include ALT, AST, ALP, total bilirubin, BUN, Serum Cr, electrolytes (K, Na, Mg, Ca and P), blood glucose and lipid profile (LDL, HDL, triglycerides).

Laboratory tests, except for the HgbA1c, will be performed during the Screening Visit and at Day 84 ±7 days, Day 168±7 days, Day 252 ±7 days and Day 336±7 days. The HgbA1c will be performed at the final visit (Day 336 or End of Study Visit).

PSA will be performed at Day 84±7 days, Day 168±7 days (prior to dosing), Day 252±7 days, and at the final visit (Day 336±7 days or End of Study Visit).

The End of Study laboratory tests, HgbA1c and PSA assessments for Protocol FP01C-13-001 will be used as the Baseline assessment for this study.

Blood samples for laboratory tests will be collected in the hospital or at the investigative site and will be sent to the Central Laboratory for analyses.

*If the patient completed 12 months of treatment with LMIS 50 mg more than 28 days prior to entering the Extension study, the testosterone level should be repeated and the repeat test should indicate that the patient maintains a castrate-level of testosterone. In addition, the ECOG, PE, ECG, laboratory and PSA tests should be repeated.

If the patient has completed 12 months of treatment with LMIS 50 mg under Protocol FP01C-13-001 within the last 28 days, they will be allowed to enter the Extension study without repeating the testosterone measurements, ECG, PE, laboratory and the PSA tests.

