5.10. Treatment for Investigational Product Overdose

The single-dose LMIS 50 mg will be carefully administered to each subject in up to two doses 6 months apart by investigators or professional clinical site personnel officially delegated that responsibility by the investigator. If any accidental overdose injection is given, the subject should be closely monitored for safety until terminated from the study.

6. Study Procedures

This is a multi-center, open-label, single-arm safety extension study. After completing 12 months of treatment with LMIS 50 mg under Protocol FP01C-13-001 (with last dose under Protocol FP01C-13-001 approximately 6 months prior to Day 0 or Protocol FP01C-13-001-EX) and providing a written informed consent, subjects will be screened against baseline inclusion/exclusion criteria necessary for study eligibility. Eligible subjects will receive LMIS 50 mg from the prefilled syringes (without dilution or other mixing) in up to two single subcutaneous injections given 6 months apart.

After a single administration on Day 0, subjects will be evaluated, blood and urine samples collected, and other procedures performed as shown in the [Table 1](#). The sign "X" indicates when the procedure should take place.

Subjects who withdraw from the study prematurely for any reason during the study period will undergo the assessments listed for the final (End of Study/Early Termination) visit. If a subject refuses to return for these assessments or is unable to do so, every effort should be made to contact him or a knowledgeable informant by telephone to determine his condition. Documentation of attempts to contact the subject should be recorded in the medical chart and CRF.

Table 1 Schedule of Assessments

	Scrn ¹ (Subjects from FP01C-13-001 who completed study more than 28 days ago)	Scrn ² (Subjects who completed the study within the last 28 days)	Treatment				ET ⁴ /EOS
Visit	1	1	2	3	4	5	6
Day (from completion of 12 months of treatment with LMIS 50 mg under FP01C-13-001)	-28-0	-28-0	0	84	168 ³	252	336
Informed consent	X	X					
Inclusion/Exclusion criteria	X	X					
Demographics	X	X					
Vital signs and height and weight ⁵ (resting 3 minutes)	X	X	X	X	X	X	X
ECOG PS	X	X					
Physical Exam	X			X	X	X	X
12-Lead ECG (Supine 5 minutes)	X				X		X
Laboratory							
Hematology ⁶	X			X	X	X	X
Biochemistry ⁷ (Fasting)	X			X	X	X	X
Urinalysis ⁸	X			X	X	X	X
HgbA1c (Fasting)	X						X
PSA	X			X	X	X	X
Testosterone	X				X ⁹		
Study treatment			X		X		

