7.2.3. Urinalysis

A urine sample will be collected for urinalysis. The urinalyses will include urine pH, specific gravity, leukocyte, erythrocyte and protein.

The urinalysis will be performed at Screening, Day 84 ±7 days, Day 168±7 days (prior to dosing), Day 252 ±7 days and Day 336±7 days (or End of Study Visit).

The End of Study urinalysis for Protocol FP01C-13-001 will be used as the Baseline

assessment for this study.

Urine samples will be collected in the hospital or at the investigative site and will be sent to the Central Laboratory for analyses.

*If the patient completed 12 months of treatment with LMIS 50 mg more than 28 days prior to entering the Extension study, the testosterone level should be repeated and the repeat test should indicate that the patient maintains a castrate-level of testosterone. In addition, the ECOG, PE, ECG, laboratory and PSA tests should be repeated.

If the patient has completed 12 months of treatment with LMIS 50 mg under Protocol FP01C-13-001 within the last 28 days, they will be allowed to enter the Extension study without repeating the testosterone measurements, ECG, PE, laboratory and the PSA tests.

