7.2.4. ECG

An ECG will be performed by standard 12-lead at the Screening Visit for eligibility and on Day 168±7 days prior to dosing and on Day 336±7 days (or End of Study Visit).

*If the patient completed 12 months of treatment with LMIS 50 mg more than 28 days prior to entering the Extension study, the testosterone level should be repeated and the repeat test should indicate that the patient maintains a castrate-level of testosterone. In addition, the ECOG, PE, ECG, laboratory and PSA tests should be repeated.

If the patient has completed 12 months of treatment with LMIS 50 mg under Protocol FP01C-13-001 within the last 28 days, they will be allowed to enter the Extension study without repeating the testosterone measurements, ECG, PE, laboratory and the PSA tests.

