10.3. Safety analysis

The transition matrix will be summarized for the following:

- Change from baseline in vital signs (BP, HR, RR)
- Change from baseline in physical examinations (including weight)

The summary results of vital signs (BP, HR, RR) and weight at Baseline, End of Study Visit, and the change from baseline will be summarized descriptively. Also the change from baseline to the End of Study Visit will be tested by paired t-test or Wilcoxon

signed-rank test at a significance level of 0.05.

The transition matrix of physical examination will be summarized.

- Change in laboratory data, including liver function (AST, ALT, ALP), renal function (BUN, Serum Cr), complete blood count with platelets, clinical chemistries (K, Na, Mg, Ca and P), urinalysis, serum glucose, and lipid profile (LDL, HDL, triglycerides) and HgbA1c

The summary results of laboratory data at the Baseline and the End of Study Visit, and change from baseline to End of Study Visit will be summarized by descriptive statistics and paired t-test or Wilcoxon signed- rank test will be used at a significance level of 0.05.

- Adverse event (AE) reporting

The analysis of adverse events will be tabulated by system organ class (SOC) and preferred terms according to the current MedDRA dictionary. Preferred terms will be used and presented as standardized tabulations by frequency and incidence rates. Adverse event incidence rates will be analyzed by severity and relationship to study drug. Any adverse event leading to death, discontinuation from the study, or change of dose will be listed as per regulation.

If any serious adverse event occurs, a brief summary about the serious adverse event will be described and listed.

- Change in 12-lead resting electrocardiograms (ECGs)

The summary results of 12-lead resting ECG at Baseline and the End of Study Visit will be summarized descriptively. The transition matrix for ECGs will be summarized.

11. Study Administrative Structure

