3.5 Endpoints

Determine the safety and tolerability by:

- 1) Assessment of clinically significant abnormal lab data, including liver function (AST, ALT, ALP), renal function (BUN, Serum Cr), complete blood count with platelets, clinical chemistries (K, Na, Mg, Ca and P), urinalysis, serum glucose, lipid profile (LDL, HDL, triglycerides) and HgbA1c
- 2) Adverse event (AE) reporting
- 3) Clinically significant changes from baseline in 12-lead resting electrocardiograms (ECGs) per the Investigator's judgment

The safety endpoints include:

- Adverse event (AE)
- Laboratory data
- Vital signs
- Physical examination
- 12-lead resting electrocardiograms (ECGs)

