10.3 Laboratory Evaluation

Clinical laboratory tests, including standard hematology, chemistry, and urinalysis:

Hematology

CBC, including Hb, Hct, RBC count, WBC count, WBC differential, platelet count and HgbA1c

Chemistry

ALT, AST, ALP, total bilirubin, BUN, Serum Cr, electrolytes (K, Na, Mg, Ca and P), blood glucose, lipid profile (LDL, HDL, triglycerides)

Urinalysis

pH, specific gravity, leukocyte, erythrocyte, protein

PSA Tumor Marker

PSA level

Testosterone Level

Testosterone level

Clinical laboratory data (hematology, biochemistry, and urinalysis) will be listed in Listings

Statistical Analysis Plan

16.2.8.2-16.2.8.4. Observations outside the normal range will be flagged. The abnormal values will be flagged with 'L' (low) for values below the lower limit of the laboratory's normal range or 'H' (high) for values above the upper limit of the laboratory's normal range. Clinically significant laboratory results will be marked as well. All original and repeated values will be listed.

The observed values of clinical laboratory data (hematology, biochemistry, and urinalysis) will be summarized for baseline, end of treatment, end of study, and change from baseline to end of treatment and end of study in Table 14.3.3.1~Table 14.3.3.3. Also, the clinical laboratory data transition status from baseline to end of treatment and end of study will be presented in Table 14.3.3.4~Table 14.3.3.6.

The PSA levels will be listed by subject in Listing 16.2.8.5; the testosterone level will be listed by subject in Listing 16.2.8.6.

Abnormal laboratory values of hematology, biochemistry and urinalysis will be listed in Listing 16.2.8.1.

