System Organ Class 1	Preferred Term 2	E	nn	(xx.x%)	E	nn	(xx.x%)	E	nn	(xx.x%)	
System Organ Class 2	Preferred Term 1	E	nn	(xx.x%)	E	nn	(xx.x%)	E	nn	(xx.x%)	
System Organ Class 2	Preferred Term 2	E	nn	(xx.x%)	E	nn	(xx.x%)	E	nn	(xx.x%)	
Death AE											
System Organ Class 1	Preferred Term 1	E	nn	(xx.x%)	E	nn	(xx.x%)	E	nn	(xx.x%)	
System Organ Class 1	Preferred Term 2	E	nn	(xx.x%)	E	nn	(xx.x%)	E	nn	(xx.x%)	
System Organ Class 2	Preferred Term 1	E	nn	(xx.x%)	E	nn	(xx.x%)	E	nn	(xx.x%)	
System Organ Class 2	Preferred Term 2	E	nn	(xx.x%)	E	nn	(xx.x%)	E	nn	(xx.x%)	

E is the number of events, n is the number of subjects, and the AE percentage: 100%*The number of subjects with event (n) / Total number of subjects in Safety population (N)
[Program: \\Foresee\\FP01C-13-001\\SAP\\Table\\S_AE.sas]

Table 14.3.2: Summary of Study Medication (Safety Population)

Variables / Status	Total (N=XX)
Received first administration	
Yes	nn (xx.x%)
No	nn (xx.x%)
Received second administration	
Yes	nn (xx.x%)
No	nn (xx.x%)
Treatment duration (days)	
n	nn
mean (SD)	xx.x (xx.x)
SE	xx.x
median (min, max)	xx.x (xx.x, xx.x)
Study duration (days)	
n	nn
mean (SD)	xx.x (xx.x)
SE	xx.x
median (min, max)	xx.x (xx.x, xx.x)

Treatment duration (days) is defined as (last administered date – first administered date + 1); and study duration (days) is defined as (last visit date – first administered date + 1).
 [Program: \\Foresee\\FP01C-13-001\\SAP\\Table\\S_EX.sas]

Table 14.3.3.1: Summary of Laboratory Assessments - Hematology (Safety Population)

Variables / Status	Total (N=XX)
Hematology at Screening (V1)	
n	nn
mean (SD)	xx.x (xx.x)
SE	nn (xx.x%)
median (min, max)	xx.x (xx.x, xx.x)
Normal	nn (xx.x%)
Abnormal - NCS	nn (xx.x%)
Abnormal - CS	nn (xx.x%)
Not Done	nn (xx.x%)
Hematology on Day 168 (V4)	
n	nn
mean (SD)	xx.x (xx.x)
SE	nn (xx.x%)
median (min, max)	xx.x (xx.x, xx.x)
Normal	nn (xx.x%)
Abnormal - NCS	nn (xx.x%)
Abnormal - CS	nn (xx.x%)
Not Done	nn (xx.x%)
Hematology on Day 336 (V6/EOS)	
n	nn
mean (SD)	xx.x (xx.x)
SE	nn (xx.x%)
median (min, max)	xx.x (xx.x, xx.x)
Normal	nn (xx.x%)
Abnormal - NCS	nn (xx.x%)
Abnormal - CS	nn (xx.x%)
Not Done	nn (xx.x%)
Hematology change on Day 168 (V4)	
n	nn

*Paired T test or Wilcoxon signed rank test will be used to test the change from baseline for continuous variables.
 [Program: \\Foresee\\FP01C-13-001\\SAP\\Table\\S_LB.sas]

Table 14.3.3.1: Summary of Laboratory Assessments - Hematology (Safety Population)

Variables / Status	Total (N=XX)

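### The protocol fixes the parent-study End of Study values as the laboratory baseline, but the SAP leaves baseline undefined and its shells use Screening (V1), where subjects entering within 28 days have no scheduled tests

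*Protocol*

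**What the plan says.** **Protocol.** Section 7.2.2 sets the rule for blood tests: "The End of Study laboratory tests, HgbA1c and PSA assessments for Protocol FP01C-13-001 will be used as the Baseline assessment for this study". Section 7.2.3 does the same for urine: "The End of Study urinalysis for Protocol FP01C-13-001 will be used as the Baseline" (assessment). Neither makes an exception for subjects retested at Screening. For ECG, section 7.2.4 says only "An ECG will be performed by standard 12-lead at the Screening Visit for eligibility", followed by the Day 168 and Day 336 recordings. It names no baseline, and 7.2.1 names none for physical examination. Section 10.3 then summarises and tests, at the 0.05 level, "The summary results of laboratory data at the Baseline and the End of Study Visit, and change from baseline to End of Study Visit".

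**Schedule (Protocol Table 1, SAP 3.4).** There are two Screening columns. The one headed "Subjects who completed the study within the last 28 days" has no mark for physical examination, ECG, hematology, biochemistry, urinalysis or HgbA1c. Footnote 2 lets these subjects enter without repeating ECG, physical examination and laboratory tests. Footnote 1 requires subjects entering after more than 28 days to repeat them.

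**SAP.** Section 4.1 tests change from baseline. Section 10.3 says laboratory data "will be summarized for baseline, end of treatment, end of study, and change from baseline to end of treatment and end of study". Section 3.5 words the ECG endpoint as a clinically significant change from baseline. No section says what baseline is. The shells for laboratory data (Tables 14.3.3.1 to 14.3.3.6), physical examination (14.3.5.1 and 14.3.5.2) and ECG (14.3.6.1 and 14.3.6.2) use Screening (V1). Section 5.2 allows no imputation.

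**The concern.** The protocol names one baseline for laboratory data and the SAP shells use another. The shells' reference visit also has no scheduled measurement for one of the two entry groups. Two competent programmers, one following the protocol and one following the shells, would produce different laboratory tables from the same data. On the literal reading, the paired laboratory and ECG tests and the informative cells of the transition tables would describe only subjects who entered more than 28 days after the parent study. One of the three listed safety endpoints, ECG change from baseline, has no defined reference in either document. The study's sole purpose is safety, so this choice should not be left until the data are in hand.

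**Working it through.** The plan gives no figure to reproduce on this point. The check sets the passages side by side.

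| Parameter (SAP shell) | Baseline named in protocol | Shell reference | Scheduled then, entry within 28 days | Scheduled then, entry after 28 days |
|---|---|---|---|---|
| Hematology, biochemistry (14.3.3.1, .2, .4, .5) | Parent End of Study (7.2.2) | V1 | No | Yes |
| Urinalysis (14.3.3.3, .6) | Parent End of Study (7.2.3) | V1 | No | Yes |
| Physical examination (14.3.5.1, .2) | None | V1 | No | Yes |
| ECG (14.3.6.1, .2) | None | V1 | No | Yes |
| Vital signs (14.3.4) | None | Day 0 | Yes | Yes |
| Weight (14.3.4) | None | V1 | Yes | Yes |

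HgbA1c falls under the 7.2.2 rule, and SAP 10.3 groups it with hematology.

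**Count of shells.**
- By conflict: 6 laboratory and urinalysis shells contradict a named baseline, and 4 physical-examination and ECG shells have none named. 6 + 4 = 10.
- By type: 4 with paired change tests (14.3.3.1 to 14.3.3.3 and 14.3.6.1), 5 transition tables (14.3.3.4 to 14.3.3.6, 14.3.5.2 and 14.3.6.2), and 1 by-visit status table (14.3.5.1). 4 + 5 + 1 = 10.

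**Effect if the shells are programmed literally.**
- *Entry within 28 days.* With no V1 value there is no laboratory or ECG change. The subject falls under *Not Done* at V1 in the laboratory and physical-examination transition tables. The ECG transition table has no such category, so the subject has no cell there.
- *Entry after 28 days.* The subject has a parent End of Study value and a V1 repeat. For laboratory tests and urinalysis the protocol selects the first and the shells select the second.

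**Illustrative size.** The share *f* entering within 28 days is not in the documents, so it is varied here as an assumption. *N* is set to the maximum of 137 in SAP 4.3. Subjects left are *n* = 137(1 − *f*), rounded to a whole number. For the same SD, the standard error of the mean change grows by √(137/*n*). The standardized paired change detectable with 80% power, assuming a two-sided 0.05 test, is (1.960 + 0.842)/√*n*.

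| *f* | *n* | SE factor | Detectable change (SD units) |
|---|---|---|---|
| 0 | 137 | 1.00 | 0.24 |
| 25% | 103 | 1.15 | 0.28 |
| 50% | 68 | 1.42 | 0.34 |
| 75% | 34 | 2.01 | 0.48 |
| 90% | 14 | 3.13 | 0.75 |
| 100% | 0 | not estimable | not estimable |

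At *f* = 50%, 137 × 0.5 = 68.5, taken as 68, and √(137/68) = 1.42. The SE factor is 1/√(1 − *f*) apart from rounding of *n*, so it hardly depends on *N*. Under the protocol's laboratory rule no early entrant is lost for this reason.

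**The case against.** The strongest reply is that V1 is shorthand and parent values will fill it for early entrants. Several points support this:
- The SAP says it rests on the protocol, which already states the laboratory rule.
- Early entrants can meet the laboratory inclusion criteria in 4.1 without a repeat test only through parent results.
- Section 7.1.2 carries parent demographic and baseline-characteristics data into this study.
- Using an observed value that the protocol designates is not imputation, so SAP 5.2 does not forbid it.

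All of this is fair, and it is why the loss of subjects is only conditional. But neither document says that parent values are loaded into V1. The listing shells offer *N/A* for laboratory tests, physical examination and ECG but not for vital signs or ECOG, which are marked in both Screening columns. That fits an empty V1 for early entrants without proving it. Even if parent values do fill V1, the laboratory conflict for later entrants remains.

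It can also be said that sections 6.1 and 7.2.1 to 7.2.4 list these tests at Screening for everyone, so some early entrants may have them. Those lists are followed by the same 28-day exemption, so such values cannot be counted on.

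Finally, the effect is limited, and this stands. Table 14.3.5.1 only reports status by visit, no protocol baseline is contradicted for physical examination or ECG, and the paired tests are unpowered.

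**Conclusion.** The concern holds and should be fixed. The mismatch between Protocol 7.2.2 and 7.2.3 and the six laboratory and urinalysis shells needs no assumption. Nor does the missing baseline definition for physical examination and ECG. The loss of early entrants from paired and transition analyses assumes that the shells are programmed literally and parent values are not imported. Its size depends on an unknown share and could be anything from nothing to everyone.

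Not affected are adverse events, vital signs (Day 0 reference), weight (V1 measured in both groups), PSA (listed only), and counts of clinically significant laboratory and ECG abnormalities at Day 168 and Day 336. No sample size or powered hypothesis depends on the point.

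**What to change.** - **Laboratory baseline.** Carry the protocol rule into the SAP, for example: baseline for hematology, biochemistry, HgbA1c and urinalysis is the FP01C-13-001 End of Study value for all subjects; repeated V1 values are listed but not used as baseline.
- **ECG and physical examination.** Name one baseline rule that uses the parent End of Study value whenever the V1 test was not repeated, and say which value applies when both exist. Using the parent value for everyone would match the laboratory rule.
- **Data source.** State that parent End of Study values are imported.
- **Shells.** Relabel Screening (V1) as Baseline in Tables 14.3.3.1 to 14.3.3.6, 14.3.5.1, 14.3.5.2, 14.3.6.1 and 14.3.6.2.
- **Minor.** Reconcile Protocol 7.2.2, which leaves HgbA1c out of Screening, with the schedule and section 6.1, which include it for later entrants.

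The cost is SAP wording, ten relabelled shells, a merge of parent-study data (assumed available, since the parent database cannot be seen from these documents) and a short protocol clarification on HgbA1c. No new visits or subjects are needed.
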